Expected Outcomes: We expect to identify 2-4 most influential HSUM factors. We will also quantify the effect size, enabling appropriate powering of a future RCT. In line with our sequential mixed-methods design, Aim 1 data will inform Aim 2 interviews.

Figure 2. Sample Composition.

[figure not shown]

Table 2. Operational Definitions of HSUM Factors.

HSUM Factors	Definition	Operational Definition
Predisposing Factors	Socio-cultural characteristics of individuals	High: ≥ 3 of the following: (1) High BC awareness (median split); (2) Low fatalism (median split); (3) Low BC worry (median split); (4) Low depression (median split); (5) Low anxiety (median split).
Enabling Factors	Logistical aspects of obtaining care	High: ≥ 3 of the following: (1) High social support (median split); (2) Household income above poverty line (yes); (3) Insured (yes); (4) MRI at usual site of care (yes); (5) Travel time to closest MRI facility (≤ 30 minutes).
Perceived Need	How women view their need for breast MRI	High: ≥ 2 of the following: (1) High perceived BC susceptibility (median split); (2) High perceived norms for BC screening (median split); (3) Provider recommendation for screening (yes); (4) More positive attitudes towards screening (median split).

C.4.b Aim 2 Overview. We will conduct semi-structured qualitative interviews with a sub-sample of Aim 1 participants (N=30). We will select information-rich cases from Aim 1 for in-depth qualitative analysis in Aim 2 (Figure 3). To do so, we will categorize Aim 1 participants based on expected and actual MRI receipt (see C.4.b.1). From participants in each group, we will gather in-depth information about their breast MRI screening decisions. The goals of Aim 2 are to (a) obtain an in-depth understanding of barriers/facilitators to MRI from the patient perspective, and (b) identify gaps in our theoretical conceptualization of breast MRI utilization.

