C.4.b.1 Aim 2 Sampling Plan. Data from Aim 1 will be used to develop individual participant profiles in order to purposively sample^{66,67} participants for in-depth interviews about their screening choices. The goal of sampling for Aim 2 is to select information-rich cases to best enhance the post-hoc modification of the conceptual model. For each HSUM category (predisposing factors, enabling factors, perceived need), Aim 1 participants will be categorized as “high” or “low” based on a priori operational definitions (Table 2). If a woman is “high” in ≥ 2 HSUM categories, she will be categorized as “yes” for expected MRI receipt (and vice versa for “no”). From expected and self-reported MRI receipt, we will create 4 utilization categories (Table 3).

C.4.b.2 Aim 2 Ascertainment and Enrollment. Participants will be randomly selected from within each utilization group and invited to interview until we have achieved our desired N. As theory-discordant women are likely to be most informative for refining our theoretical model, we will over-sample women in these groups (n=10 per group) compared to the concordant groups (n=5 per group). If there are insufficient numbers in any group to allow for examination in Aim 2, we will continue Aim 1 surveys until we achieve our desired N.

C.4.b.3 Aim 2 Procedures. Interviews will take place via phone. All interviews will be conducted by a research assistant (RA) with prior experience conducting qualitative interviews. The site PIs ([name] and [name]) will review 10% of interview recordings at random to ensure high quality/fidelity in the data collection. The interviews will be guided by the HSUM (Table 4). We will start with a broad overview of patients’ experiences with screening breast MRI, followed by probing questions to address specific HSUM components. Patients will also be queried regarding Aim 1 survey responses. Upon completion, interview participants will receive a \$20 gift card. Our team has extensive experience in conducting qualitative interviews^{68,69} and will be supported by experts in qualitative research from MCC’s PRISM Core.

Upon completion of both study aims, all participants will be sent (via mail or email) educational materials about breast MRI and screening recommendations, as well as a list of American College of Radiology (ACR) accredited breast MRI screening facilities in the greater Tampa Bay region or the Washington DC metro area, as appropriate.

C.4.b.4 Aim 2 Analytic Approach.

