Data Management and Analysis:

Interviews will be transcribed verbatim. The research team will analyze the transcript themes through open coding, axial coding, and selective coding.⁷⁰ The PI and RA will separately examine transcripts and inductively generate themes from the data, drawing on the conceptual model, to produce a codebook. We will present themes and codebook to our interdisciplinary team and the CAB, then iteratively revise our approach to enhance validity.⁷¹ Once consensus is reached, this codebook will be uploaded into MAXQDA (a qualitative data analysis software program) and be systematically applied to the data. To ensure coding scheme reliability, the PI and RA will code 10% of transcripts independently, and Krippendorff’s alpha will be calculated with the goal of achieving $\alpha \geq 0.70$ (an acceptable level of agreement).⁷² Following achievement of $\alpha \geq 0.70$, the remainder of the data will be split between the two coders for analysis.

Sample Size. We will follow the principle of theoretical saturation and continue interviews until no new information is obtained.⁷³ Based on our prior research^{68,69} we anticipate 5-10 interviews will be required to reach saturation. Thus, we aim to interview 10 participants per discordant group and 5 participants per concordant group, for 30 interviews total.

Table 4. Sample Questions for Aim 2 Qualitative Interviews.

HSUM Factor	Sample Questions
Predisposing Factors	Not all women at high risk for breast cancer receive breast MRIs. What are some characteristics of people that may affect whether or not they have a breast MRI?
Enabling Factors	Not all women at high risk for breast cancer have the ability to seek breast MRI if needed. What are some factors that may affect whether or not a woman can seek MRI screening?
Perceived Need	For a woman to get breast MRI screening, she first has to know that she needs one. What are some factors that may affect whether or not a woman thinks she needs a breast MRI?
Screening Concordance	In the survey you completed, your answers were most similar to those of women who do (not) get breast MRIs. This is (in)consistent with your screening history. Do you think that there are any other factors that we missed that affected whether or not you had a breast MRI?

Table 3. MRI Utilization

Group	Expected MRI Receipt Based on HSUM	Self-Reported MRI Receipt
Concordant Doers	Yes	Yes
Discordant Doers	No	Yes
Discordant Non-Doers	Yes	No
Concordant Non-Doers	No	No

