These studies do not involve any deception. Informed consent and consenting procedures will adhere to the Advarra IRB and the MedStar/Georgetown University Joint Oncology IRB guidelines. All subjects will sign consent forms prior to their participation. They will be asked to review the consent form prior to signing and will be provided the opportunity to ask any questions. Participant consent is ongoing, and all will be informed that they do not have to participate. If a person is not eligible or if she decides that she is no longer interested, the informed consent (or the remainder of the assessment) will end. Consent in minors is not applicable, as participants less than 25 years old are not eligible for the present study.

In Aim 1, participants will be self-identified. We will use five different recruitment strategies to enroll 300 participants, as described in Section 2.5 ("Recruitment and Retention Plan"). Once identified, potential participants will be assessed for eligibility using the NCI BCRAT; this method has been successfully used to identify high risk women in our prior studies and by our consultant, [name], in her large, population-based studies of women at high risk for BC.^{46,47} Eligible women will provide informed consent via forms mailed and returned with the survey materials or via electronic signature on web-based forms, as preferred.

In Aim 2, participants will be selectively sampled from Aim 1. Women will be randomly sampled and invited to participate in Aim 2 interviews until we achieve n=30 participating women.

Participants will be asked to provide their contact information for potential future follow-up at the end of the Aim 1 survey. Participants will be contacted using their preferred method. Upon confirmation of interest, participants will be sent two copies of the informed consent, one of which will be signed and returned to MCC or LCCC (depending on site of recruitment). Thus, informed consent will be documented by signature on forms approved by the Advarra IRB and the MedStar/Georgetown University Joint Oncology IRB.

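### The sample Screening Concordance question in Table 4 tells a woman whose answers hers resembled, but the Aim 2 grouping rule never makes that comparison

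*Combined protocol and SAP*

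**What the plan says.** Section C.4.b.1 scores each Aim 1 participant high or low in three HSUM categories, "based on a priori operational definitions (Table 2"). The Table 2 items are median splits, for example "1) High BC awareness (median split); (2) Low fatalism (median split); (3) Low BC worry (median split"), or fixed criteria such as being insured or having a provider recommendation. A woman who is high in at least two of the three categories is assigned an expectation: "she will be categorized as “yes” for expected MRI receipt". Only then is actual receipt brought in: "From expected and self-reported MRI receipt, we will create 4 utilization categories (Table 3"). Table 3 labels the expectation as one based on the HSUM.

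Section C.4.b.2 plans 10 interviews in each of the two discordant groups and 5 in each of the two concordant groups.

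The sample question in Table 4 opens with "In the survey you completed, your answers were most similar to those of women who do (not) get breast MRIs". It then tells the woman whether this agrees with her screening history, and ends: "Do you think that there are any other factors that we missed that affected whether or not you had a breast MRI".

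**The concern.** The opening sentence reports an empirical finding: that this woman's answers were compared with those of women who had, or did not have, an MRI, and fell closer to one set. What the study holds is a prediction from theory. The two can differ, and Aim 2 exists to explore where they do.

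Placement makes this matter. Aim 2 is meant to find barriers and facilitators that the HSUM leaves out, and this is the only item in Table 4 that asks what was missed. It is also the only one put in terms of the woman's own MRI decision; the other three ask about women or people in general. Just before answering, she hears an unsupported statement about whom she resembles and a judgement on whether her behaviour fits. That could colour what she says, and the colouring would differ between discordant and concordant groups. Once the interviews are done, it cannot be removed.

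**Working it through.** **Planned interviews.** From C.4.b.2: 2 × 10 + 2 × 5 = 30, which reproduces the stated total. The discordant groups supply 20 of 30 (67%). With the wording as it stands, those 20 would be told of a mismatch and the other 10 of a match.

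**What enters the grouping, in order.**
1. Item scores (Table 2): median splits or fixed criteria. The group whose median is used is not stated, but no item is split by MRI receipt.
2. Category scores (Table 2): at least 3 of 5 predisposing items, at least 3 of 5 enabling items, at least 2 of 4 perceived-need items.
3. Expected receipt (C.4.b.1): high in at least 2 of 3 categories.
4. Self-reported receipt (Table 3): cross-classified with step 3.

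Steps 1 to 3 contain no information on how women with or without an MRI answered. The Aim 1 logistic regression (C.4.a.5) relates HSUM predictors to health behaviors, but it is not used for grouping. No step yields a similarity statement.

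**The label need not follow resemblance to recipients.** Two profiles possible under Table 2's 14 items (5 + 5 + 4):
- Woman A meets 3 predisposing items, 3 enabling items (social support, income, insurance) and no perceived-need item. She meets 6 of 14, is high in two categories, and is expected *yes*. She has no provider recommendation, no MRI at her usual site, and travels more than 30 minutes.
- Woman B meets 2 predisposing items, 2 enabling items (MRI on site, short travel) and all 4 perceived-need items, including a recommendation. She meets 8 of 14, is high in one category, and is expected *no*.

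A would be told that she resembles women who get MRIs, and B that she resembles women who do not. In the team's own pilot (C.3.c), 4 of the 6 women who had an MRI gave a physician recommendation as the reason. The background section also describes screening rising with anxiety until anxiety becomes too intense, whereas Table 2 counts only low anxiety as favourable.

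**Illustration on assumed inputs.** The documents give no item prevalences or effects. I assumed independent items; 50% at each median split; income above poverty 85%, insured 90%, on-site MRI 50%, short travel 60%, recommendation 35%; and 25% MRI receipt. In 400,000 simulated women I compared the count rule with a direct similarity rule: is her standardised item profile nearer the mean of recipients or of non-recipients? The count rule labels about 72% *yes*. The two rules disagree for:
- 29% of women if all 14 items act equally (OR about 1.5 each)
- 42% if only awareness, on-site MRI and recommendation matter (OR about 2.5 each)
- 48% if only recommendation matters (OR about 7.4)

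These are shares of all simulated women, not of interviewees, and they depend on how similarity is defined. They show that disagreement is plausible; they do not estimate it for this study.

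**The case against.** The heading reads "Table 4. Sample Questions for Aim 2 Qualitative Interviews", so this is an example for a semi-structured interview, not a fixed script. Section C.4 says the interview guides will be designed using Aim 1 data, and the final guide is not in the documents. Section C.4.b.3 already begins with a broad account of the woman's experience, then HSUM probes, and also plans to ask about her survey answers. If the Table 4 order is followed, the concordance item comes last, after unprompted material has been collected. Its closing question is open and names no factor. Raising a mismatch is also a reasonable way to learn from theory-discordant women, who are over-sampled for that purpose.

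Most of this stands. It limits the point to wording and order, and it means one cannot say that all 30 women will hear the sentence. It does not supply the missing comparison, and nothing in the plan commits to changing the sentence.

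Three stronger readings are tempting but not supported:
- *The sentence is untrue for many women.* A reader might note that, at about 25% receipt, most women labelled *yes* would not have had an MRI. That is a base rate. It does not show whose answers a woman's resemble; a sound similarity rule could give the same picture.
- *The sentence contradicts the consent section's* "These studies do not involve any deception". Loose wording for a model-based expectation is not shown to be intentional misleading.
- *The prompt is shown to create the contrast between groups.* An effect on answers is plausible but not demonstrated, and the analysis section specifies no formal between-group comparison of themes.

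**Conclusion.** The concern holds in limited form. The similarity statement has no basis in the grouping rule; this follows from Table 2, C.4.b.1 and Table 3 alone and needs no assumed figure. The statement may be true where the HSUM items do track receipt, and may be false for some women. How many cannot be determined from the documents.

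The reach is one sample question, which by design would deliver a mismatch message in up to 20 of 30 interviews if used as written. That any answers would be altered is a judgement about interviewing. No sample size, power statement, grouping or Aim 1 estimate is affected. It is still worth correcting before Aim 2 starts, because the item is the one most directly tied to Aim 2's research question and the change is cheap.

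**What to change.** In the final interview guide:
1. Ask first, with no reference to group: *Thinking about your own decision, what affected whether you had a breast MRI, and what did our survey not ask about?*
2. Only after that, if feedback is kept, say what the rule does: *Based on your survey answers, the model we are using would have expected you to have (not have) a breast MRI. What might it have missed?*
3. Delete the sentence about whose answers hers were most similar to.

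Do not rescue the sentence by basing the feedback on the fitted Aim 1 model. The groups are defined by the a priori rule, so model-based feedback could tell a woman sampled as discordant that she is consistent. C.4.b.2 also allows Aim 1 surveys to continue when a group is short, so a final fitted model may not exist before all interviews.

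The cost is one reworded item and a routine IRB submission of the guide.
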